#### 4.4.1 Participant Registration

All participants must sign the consent form prior to determination of eligibility for this study. Participants eligible for interferon therapy will complete the interferon education packet and review their answers with the study team and convince the study team that they answered the questions accurately or understand the correct answers. Registration information, the eligibility checklist with supporting documentation, and the on-study case report form for potential participants at institutions other than UVA must be received by the UVA HITC prior to registration and randomization. All participants who meet the inclusion/exclusion criteria may be registered to the study. Registration will occur following verification of eligibility by the treating physician or institutional Pl.

#### 4.4.2 Randomization

Randomization will be discussed with participants during the process of informed consent, and informed consent must be documented prior to randomization. Randomization will occur after registration and no sooner than 5 days prior to the start of treatment. In part 1, randomization will be based on equal allocation among allowable arms unless a weighted allocation scheme is triggered (section 9.2.1). Randomization will not be stratified by

institution. The randomization codes are generated by the study statisticians and stored in the Cancer Center Clinical Trials Database. The UVA HITC will communicate with the outside site to let them know which study arm a participant has been randomized to. Participants should receive the first scheduled vaccination or biopsy (if applicable) within 2 weeks of registration. Part 2 will not include randomization.

# 4.4.3 Management of Participants

This study will be conducted on an outpatient basis, with participants scheduled to be evaluated on days 1, 8, 15, 22, 36, 43, 57, 78, and 85, and week 26 (or more often if needed for testing or medical reasons). As needed, there may also be follow-up within 1-3 weeks after biopsies performed on days 8 or 22 for wound evaluation. Participants will also be followed-up at 52 weeks (1 year) and at 2 years with blood draws for studies of immune response durability. During off treatment follow-up, participants will be followed yearly for survival and disease status.

# 5.0 STUDY MEDICATION FORMULATION, DOSAGE, ACCOUNTABILITY AND ADMINISTRATION

## 5.1 Study Medication Formulation

# 5.1.1 Peptide Synthesis and Storage

All peptides are synthesized directly from amino acids, and then are purified by high performance liquid chromatography (HPLC). The identity of the synthetic peptides will be confirmed by verifying their mass and amino acid sequences by mass spectrometry. Details of the synthesis, certificates of analysis, and technical summaries are included in the Chemistry and Manufacturing section of the IND application. Each bulk peptide is supplied as lyophilized pow der without excipients and stored at a temperature  $\leq$  -70°C and protected from light.

## 5.1.2 Preparation of peptide vaccine vials for patient use.

For the 6 peptides prepared at UVA, the bulk peptides are solubilized in aqueous solution, sterile-filtered, and mixed to provide a final concentration of 600 mcg/ml for each of the 6 peptides. The peptide mixture is then aliquoted at 1 ml per vial into sterile borosilicate vials in the HITC clean room. The mixture is slightly cloudy, as the pH of the mixture supports solubility of most of the peptides, but some peptides are partially in suspension at that pH. The 7th peptide, from NY-ESO-1 is provided as single use vials of lyophilized peptide, at 600 mcg/vial, from the Ludwig Institute for Cancer Research, prepared under GMP conditions.

#### 5.1.3 Storage of Vialed Peptides

The vials of peptide are stored by the HITC at a temperature  $\leq$  -70°C and protected from light. On the day of use, they are thawed at room temperature or in a water bath up to 37°C. They should be swirled gently as they are thawed and moved to a refrigerator as soon as they are thawed if not being injected immediately. Once thawed, the vial(s) must be used for preparation of the vaccine within 24 hours.

### 5.1.4 Lot Testing

Each lot of peptide vaccine is evaluated as required by the FDA to confirm identity, sterility, general safety, purity, lack of peptide aggregation and is tested for endotoxin. In addition,

Version Date: 07-31-17

studies of stability will be performed over time. The details of these tests are outlined in Appendix 5.

# 5.1.5 Labeling

The labeling of vials will occur as specified below.

Each vial of lyophilized peptide is labeled with the following information:

Short name of the product: "LPV6"

Product number

Proper name of the product: "6 long melanoma peptides" Name and address of the vialing facility: "UVA-HITC"

Lot number

Date of manufacture (the date of vialing the reconstituted peptides)

Serial number

Quantity of each peptide per vial: 600 mcg/ml Vial contains no preservative, store at ≤ -70°C

"Caution: New Drug - Limited by US Federal law to investigational use"

# 5.2 Preparation, Dosage, and Storage of Study Drug

# 5.2.1 Dosage and Preparation of Peptide Vaccine

#### Part 1:

The peptides will be prepared by combining the LPV6 mixture of 6 peptides with one NY-ESO-1 long peptide. The long melanoma peptides (LPV6) will be available as single-use vials of 1 ml volume containing 600 mcg/ml of each peptide. The NY-ESO-1 peptide is provided as lyophilized preparation with 600 mcg of peptide in single use vials. The tetanus peptide is vialed as 300 mcg lyophilized peptide per vial. For each vaccine, the full 1 ml of the peptide solution of LPV6 (600 mcg) will be withdrawn and injected into the vial of lyophilized NY-ESO-1 peptide, creating a solution/suspension of all 7 long peptides, each at 600 mcg/ml. Then 0.75 ml of this suspension/solution will be withdrawn and injected into one vial of lyophilized tetanus peptide, to create a suspension/solution of 450 mcg of each of the 7 long peptides, and 300 mcg of tetanus peptide in 0.75 ml. Then, the full 0.75 ml of this solution/suspension (450 mcg of all 7 long peptides, plus 300 mcg tetanus peptide) will be withdrawn into a syringe for injection as specified below for each study arm. Details of making emulsions with IFA (Montanide ISA-51) are provided in the Investigator's Brochure and Study Manual.

#### Part 2:

The peptides will be prepared by combining the LPV6 mixture of 6 peptides with one NY-ESO-1 long peptide. The long melanoma peptides (LPV6) will be available as single-use vials of 1 ml volume containing 600 mcg/ml of each peptide. The NY-ESO-1 peptide is provided as lyophilized preparation with 600 mcg of peptide in single use vials. For each vaccine, the full 1 ml of the peptide solution of LPV6 (600 mcg) will be withdrawn and injected into the vial of lyophilized NY-ESO-1 peptide, creating a solution/suspension of all 7 long peptides, each at 600 mcg/ml. Then 0.75 ml of this solution/suspension (450 mcg of all 7 long peptides) will be withdrawn into a syringe for injection as specified below for each study arm. Details of making emulsions with IFA (Montanide ISA-51) are provided in the Investigator's Brochure and Study Manual.

**Study Arm A (IFA)**: Sterile saline solution 0.75ml will be added to 0.75 ml of LPV7 + tetanus peptide (total 1.5 ml). This will be combined with 1.5 ml of Montanide ISA-51VG to create an emulsion. Two (2) ml will be injected half-intradermally and half-subcutaneously in one skin location.

**Study Arm B (polyICLC)**: PolyICLC (Hiltonol) is provided from Oncovir, Inc. (Washington, D.C.) as a clinical grade reagent for experimental use in single-use vials containing 1 mL of a 2 mg/mL solution. We will administer 1 mg (0.5 ml) per vaccine. PolyICLC (Hiltonol) 0.75 ml will be added to 0.75 ml of LPV7 + tetanus peptide. One (1) ml of this will be injected half-intradermally and half-subcutaneously in one skin location.

**Study Arm C (resiquimod)**: Resiquimod is provided by 3M (Minneapolis, MN) and is packaged in multi-dose tubes (typically 3 g of 0.2% gel). Sterile saline solution 0.75ml will be added to 0.75 ml of LPV7 + tetanus peptide. One (1) ml of this will be injected half-intradermally and half-subcutaneously in one skin location. Immediately after vaccine injection, apply approximately 500 mg of 0.2% resiquimod gel with a gloved finger over a 25 cm² area of the skin at the vaccine site. Rub the gel into the skin for 1 minute until it vanishes. Following application, the site may be covered with an occlusive dressing, such as Tegaderm, for about 8 hours. Participants are encouraged to wash the area at 8 hours after application.

**Study Arm D (polyICLC + resiquimod)**: PolyICLC (Hiltonol) 0.75 ml will be added to 0.75 ml of LPV7 + tetanus peptide. One (1) ml of this will be injected half-intradermally and half-subcutaneously in one skin location Immediately after vaccine injection, apply approximately 500 mg of 0.2% resiquimod gel with a gloved finger over a 25 cm² area of the skin at the vaccine site. Rub the gel into the skin for 1 minute until it vanishes. Following application, the site may be covered with an occlusive dressing, such as Tegaderm, for about 8 hours. Participants are encouraged to wash the area at 8 hours after application.

**Study Arm E (IFA + polyICLC):** Part 1: PolyICLC (0.75 ml) will be added to 0.75 ml of LPV7 + tetanus peptide (total 1.5 ml). This will be combined with 1.5 ml of Montanide ISA-51VG to create an emulsion. Two (2) ml will be injected half-intradermally and half-subcutaneously in one skin location.

Study Arm E2 (IFA + polyICLC): Part 2: PolyICLC (0.75 ml) will be added to 0.75 ml of LPV7 (total 1.5 ml). This will be combined with 1.5 ml of Montanide ISA-51VG to create an emulsion. Two (2) ml will be injected half-intradermally and half-subcutaneously in one skin location (as in study arm A).

Study Arm F (IFA + resiquimod): Sterile saline solution 0.75ml will be added to 0.75 ml of LPV7 + tetanus peptide (total 1.5 ml). This will be combined with 1.5 ml of Montanide ISA-51VG to create an emulsion. Two (2) ml will be injected half-intradermally and half-subcutaneously in one skin location (as in study arm A). Immediately after vaccine injection, apply approximately 500 mg of 0.2% resiquimod gel with a gloved finger over a 25 cm² area of the skin at the vaccine site. Rub the gel into the skin for 1 minute until it vanishes. Following application, the site may be covered with an occlusive dressing, such as Tegaderm, for about 8 hours. Participants are encouraged to wash the area at 8 hours after application.

Study Arm G (IFA + polyICLC + resiguimod): PolyICLC (0.75 ml) will be added to 0.75 ml of LPV7 + tetanus peptide (total 1.5 ml). This will be combined with 1.5 ml of Montanide ISA-51VG to create an emulsion. Two (2) ml will be injected half-intradermally and half-subcutaneously in one skin location (as in study arm A). Immediately after vaccine and polyICLC injection, apply approximately 500 mg of 0.2% resiguimod gel with a gloved finger over a 25 cm² area of the skin at the vaccine site. Rub the gel into the skin for 1

minute until it vanishes. Following application, the site may be covered with an occlusive dressing, such as Tegaderm, for about 8 hours. Participants are encouraged to wash the area at 8 hours after application.

# Storage of Prepared Peptide Vaccines

The prepared peptide vaccines will be stored in a plastic syringe and delivered to the clinicians in a plastic bag. This bag with the syringe will be stored at room temperature until the vaccine is administered. Ideally, the vaccine should be administered within 1-2 hours after mixing. If the vaccine is not administered within 4 hours after mixing, it should be discarded.

# 5.3 Drug Accountability and Distribution

Study drug will be accounted for and distributed to UVA patients and the outside sites using the HITC InvestMed Database. The InvestMed Database is an Access database that interfaces with the Cancer Center Clinical Trials clinical database so that drug may be allocated and dispensed on a per patient basis to UVA patients. For the outside sites, drug is dispensed to the corresponding institution and tracked on a per institution basis. Study drug will be sent to the outside sites by HITC personnel.

## 5.4 Administration of Vaccines

# 5.4.1 Designation of Vaccine Sites

Evidence suggests nodes proximal to a tumor site may be relatively immunosuppressed ; therefore, the vaccination sites will be distant from sites of known tumor whenever possible. In general, participants will be vaccinated in upper arm or thigh locations. If a participant has received a prior experimental vaccine, vaccines should not be administered at the same site as the prior experimental vaccine, but they may be administered on the same extremity as prior vaccines.

#### 5.4.2 Regimen

Part 1: Each vaccine will be administered at a different site, rotating among available extremities when possible.

Part 2: The same skin location will be used for all vaccines. If the vaccine site has severe inflammation or ulceration after multiple vaccines, the next vaccine may be placed adjacent to the original site.

Chronic inflammatory reactions at the vaccine sites are expected to occur in all participants who receive Montanide ISA-51. Induration may persist for days to months, but is not expected to require additional therapy. Sterile abscesses may occur in some participants. These are not a basis for discontinuation of the vaccines. However, if the inflammatory reactions develop significant ulceration of the skin (> 2 cm), then this would be considered a dose-limiting toxicity and the patient would be taken off the study.

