### 5.5.2 Discontinuation

If participants are discontinued prior to one or more scheduled skin biopsies, they will not receive those biopsies. Protocol treatment will be discontinued for any of the following reasons:

- 5.5.2.1 Any dose-limiting toxicity as defined in Section 7.4.
- 5.5.2.2 In circumstances where assessment of an AE is limited, such as by intercurrent illness, or when laboratory studies are required to assess for other causes of toxicity, the vaccine/biopsy schedule may be interrupted for up to 7 days. Delay of one vaccine administration, biopsy, or evaluation visit by up to 7 days will not be considered a protocol violation, regardless of attribution. If more than one vaccine is delayed by 8 days or more, treatment must be discontinued.
- 5.5.2.3 Disease progression requiring other therapy (e.g. surgery under general anesthesia, radiation, chemotherapy, or steroid therapy). The appearance of small metastases or recurrent tumor deposits will not be a basis for discontinuing the vaccinations. Biopsy to determine the nature of new lesions, or minor surgical procedures to excise a new lesion, will not be a basis for discontinuing vaccinations.

- 5.5.2.4 Initiation of cytotoxic chemotherapy, radiation therapy, steroid therapy as detailed under Section 4.2.5, or other immunosuppressive therapy.
- 5.5.2.5 Any other potential adverse reaction deemed sufficiently serious to warrant discontinuation of therapy by the Principal Investigator or one of the sub-investigators.
- 5.5.2.6 Noncompliance with the requirements of the study.
- 5.5.2.7 Therapy may be discontinued at the participant's request.
- 5.5.2.8 Therapy may be discontinued at the discretion of an investigator.
- 5.5.2.9 Pregnancy. Pregnant participants will continue to be followed for the duration of the pregnancy.

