#### 5.5.3 日ective Withdraw al

A participant who is enrolled but neither receives any study drug nor has a skin biopsy on protocol may be replaced. Every attempt will be made to evaluate any data from these participants for endpoint assessment.

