# 5.5.4 Delayed Visit for Reasons Other Than Toxicity

A schedule for return visits should be established at the first visit. If a participant misses a treatment, the missed treatment will be administered as soon as possible, so that the subsequent vaccinations are given in the appropriate intervals. Treatment may be continued for an additional time period, if needed. Participants who are vaccinated outside of the established schedule should return to the original schedule as soon as possible.

The table below defines what constitutes a delayed visit, whether the participant should continue to be treated, and whether a protocol violation/deviation should be reported and recorded. The range of days is counted from the original scheduled date.

Table 6. Delayed Visit for Reasons other than Toxicity				
Treatment Period	Range of Days	Participant Treatment	Protocol Deviation	
Vaccine 1				
Day 1	± 2 days	Vaccine/Labs	No	
	± 3 to 7 days	Vaccine/Labs	Yes	
	± 8 or more days	Labs	Yes	
Vaccine 2/Biopsy*				
Day 8	± 2 days	Vaccine/Labs/Biopsy	No	
	± 3 to 7 days	Vaccine/Labs/Biopsy	Yes	
	± 8 or more days	Labs	Yes	
Vaccine 3*				
Day 15	± 2 days	Vaccine/Labs	No	
	± 3 to 7 days	Vaccine/Labs	Yes	

	± 8 or more days	Labs	Yes
Assessment/Biopsy			
Day 22	± 2 days	Biopsy/Labs	No
	± 3 to 7 days	Biopsy/Labs	Yes
	± 8 or more days	Labs	Yes
Assessment			
Day 43	L O dovo	Labs	No
	± 2 days	1 1 1	
	± 3 to 7 days	Labs	Yes
	± 8 or more days	Labs	Yes
Vaccines 4-6*			
Days 36, 57, 78	± 7 days	Vaccine/Labs	No
	± 8 to 14 days	Vaccine/Labs	Yes
	± 15 or more days	Labs	Yes
Assessment			
Day 85 (Week 12)	± 7 days	Labs/Scans	No
	± 8 to 14 days	Labs/Scans	Yes
	± 15 or more days	Labs	Yes
Follow-up			
Week 26, Year 1 and 2	± 7 days	Scans/Labs	No
	± 8 to 30 days	Scans/Labs	Yes

A participant will be taken off protocol treatment if more than one vaccination is delayed [ $\pm$  3 to 7 days] during the treatment period.

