#### 6.3 Tumor tissue collection

If during the study, participants develop metastases or recurrences, these may be removed, and following receipt by pathology, may be evaluated by the study research team. Tissue samples may be screened for antigen expression or protein profiles using tests such as Western blots, immunohistochemistry, PCR, flow cytometry or gene chip analysis. Tumor escape mechanisms may also be evaluated. Specimens will be used in immunological assays to assess T cell function or antibody response. Assays generally used for this type of testing include, but are not limited to, Elspot assays, ElSAs, chromium-release assays, proliferation assays and intracellular cytokine staining. Specimens may be used to study the immunologic aspects of the tumor microenvironment or as targets or controls in laboratory assays. Specimens may be used to establish cell lines for long-term studies.

This tissue may also be compared to lesions resected prior to enrollment, which will be requested from the pathology department of each institution as paraffin-embedded tissue samples, and these tissues may be banked for use in future studies. If participants are removed from the study or progress during or after follow-up, tissue may be collected for use as part of this study, as described above, or banked for use in future studies

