Injection site reaction/induration was experienced at maximum grade 3 in 5% of patients in Arm A of Mel44. Ulceration was experienced as maximum grade 3 in 7% of patients in Arm A of Mel 44. By the rule above (observed in  $\geq$ 5% of treated patients), injection site reaction, induration, and ulceration would be expected at grade 3. Despite this and in the interest of the patients, we would consider grade 3 injection site reaction with significant ulceration of the skin ( $\geq$  2 cm) as a DLT (see section 7.8).

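### Section 5.4.2 takes a participant with vaccine-site ulceration above 2 cm off the study, while Section 5.5.2 stops only treatment; read literally, 5.4.2 loses later blood draws

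*Combined protocol and SAP*

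**What the plan says.** Section 5.4.2 covers where injections go in each part and what site reactions to expect. For Part 2 it foresees trouble at the single site: "If the vaccine site has severe inflammation or ulceration after multiple vaccines, the next vaccine may be placed adjacent to the original site". It says that sterile abscesses are no reason to stop vaccines. For ulceration above 2 cm it then says: "then this would be considered a dose-limiting toxicity and the patient would be taken off the study".

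Section 5.5.2 introduces its list with "Protocol treatment will be discontinued for any of the following reasons", and the first item is any DLT. The only procedure it says is lost is biopsy: "If participants are discontinued prior to one or more scheduled skin biopsies, they will not receive those biopsies". Section 5.5.4, on delays unrelated to toxicity, uses the narrower term: "A participant will be taken off protocol treatment if more than one vaccination is delayed".

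The Endpoints section of the Protocol Precis makes the CD8 response in blood, at its peak and at week 26, a primary endpoint. Under Section 9.7.2, one measurable post-treatment sample makes a participant evaluable, and peak response uses blood up to week 12. Section 9.5.2 sets 16 eligible participants for Part 2 and reads 12 or more responders as support for same-site injection.

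**The concern.** One event has two written consequences. Staff dealing with a badly ulcerated site would naturally turn to 5.4.2, because that is where site reactions are described. If they apply it as written, the participant leaves the study. Adverse-event follow-up then ends early, and blood needed for both primary immunologic endpoints is not drawn.

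The two endpoints are affected differently. At week 26 the participant has no sample. For peak response, a participant with one earlier measurable sample stays in the denominator with fewer chances to be scored a responder, so the observed rate can only move down. Section 5.5.3 does not offer a substitute, since "A participant who is enrolled but neither receives any study drug nor has a skin biopsy on protocol may be replaced" and this participant has had vaccine. In a cohort of 16, each participant is 1/16 = 6.25 percentage points.

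**Working it through.** **1. Which reading do the other sections support?**

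- *Off treatment only.* Section 5.5.2 stops treatment and drops only biopsies. Section 5.5.4 has a separate term for stopping vaccines. Table 6 keeps labs at visits too late for the vaccine, although it concerns delays unrelated to toxicity. Section 7.4.2 has adverse events followed until they resolve or stabilise, and related events recorded until treatment follow-up is complete. Appendix 1 puts days 183, 365 and 730 under follow-up, apart from active treatment.
- *Not settled.* Section 6.3 treats removal from the study as a state of its own and provides only for tissue: "If participants are removed from the study or progress during or after follow-up, tissue may be collected for use as part of this study". Section 4.4.3 describes off-treatment follow-up as yearly, for survival and disease status. No section says that blood draws continue after a DLT.

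**2. What the literal reading loses.** The peak-window draws after the first vaccine are on days 8, 22, 43 and 85 (Section 6.2, Appendix 1).

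| Removal | Peak-window draws lost | Later draws lost |
|---|---|---|
| Day 15 | 3 (days 22, 43, 85) | weeks 26, 52, 104 |
| After the day-22 draw, or day 36 | 2 (days 43, 85) | weeks 26, 52, 104 |
| After the day-43 draw, to day 78 | 1 (day 85) | weeks 26, 52, 104 |

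Section 5.4.2 expects ulceration after several vaccines, so the lower rows are more likely. A response already recorded still counts.

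**3. The plan's own figure.** The one-sided 80% Clopper-Pearson lower limit for 12/16 is the 0.20 quantile of Beta(12, 5), which is 0.6155. This agrees with the 61.5% in 9.5.2. For 11/16 it is the 0.20 quantile of Beta(11, 6), which is 55.1%. One lost responder at the margin therefore misses the rule.

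**4. How many participants.** The documents give no rate for ulceration above 2 cm. I assume that it equals the grade 3 ulceration rate in prior trials: 2% in Mel58 and 6% in Mel44 (Table 5), and 7% in Mel44 Arm A (Section 7.4.3: "Ulceration was experienced as maximum grade 3 in 7% of patients in Arm A of Mel 44").

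- Expected cases: 16 × 0.02 = 0.32; 16 × 0.06 = 0.96; 16 × 0.07 = 1.12.
- Chance of at least one: 1 − 0.98^16 = 28%; 1 − 0.93^16 = 69%.

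For comparison, 9.6.2 reports 1/16 DLTs of any kind on Arm E, with rotating sites.

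**5. Illustration of the effect on the 12/16 rule.** Let one participant's chance of an observed response fall from r to q because draws are lost, with the other 15 at a true rate of 75%. The fall in P(at least 12/16) is (r − q) × P(Bin(15, 0.75) = 11) = (r − q) × 0.225.

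- 75% to 60%: 0.15 × 0.225 = 0.03.
- 50% to 25%: 0.25 × 0.225 = 0.06.
- 75% to zero (ceiling): 0.75 × 0.225 = 0.17.

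All r and q values are assumptions, because the documents give no response rate after shortened vaccination. The results are conditional on one affected participant and on the literal reading being applied, so they are not expected losses.

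**The case against.** The strongest reply is that this is a loose phrase in a section on giving injections, and that the rest of the protocol outweighs it. Sections 5.5.2 and 7.4.2 and the layout of Appendix 1 all point to stopping treatment and continuing follow-up. Under 7.4.2, treatment follow-up closes early only when the participant receives additional treatment, so someone who simply stops vaccines still fits it. That stands, and it makes the literal reading unlikely. It does not remove the conflict, because none of those places says in terms that the draws continue.

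It is also fair that the numbers lean on assumptions. The 6% and 7% rates come from Mel44, graded under CTCAE v3 according to Table 5. The v4-graded figure is 2%, or about 0.3 cases. The ceiling of 0.17 needs the chance of an observed response to fall to zero, although by the time of most removals days 8 and 22 would already have been drawn. No threshold is set for week 26, so a missing sample there costs a little precision.

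Two stronger readings are tempting. A reader might infer that the plan deliberately discards primary-endpoint data after a DLT; 5.5.2 and 7.4.2 contradict that. A reader might also infer that no accrual allowance covers such a removal. The Accrual paragraph of the Protocol Precis applies the 18-for-16 allowance to ineligibility, dropout and withdrawal, and Section 7.6.4 treats dropping out because of an adverse event as a withdrawal or dropout. The documents do not support a complaint about accrual.

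**Conclusion.** The inconsistency between 5.4.2 and 5.5.2 is real and in the current text. The likely intent is to stop treatment only. Applied literally, 5.4.2 would end adverse-event follow-up early and lose the week 26, 52 and 104 samples and any peak-window draws still due, while the participant stays in the peak-response denominator.

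The size is small: about one participant or none, conditional on the 2–7% proxy and on staff following the literal wording, a chance that cannot be estimated from the documents. Part 2 is a pilot, and by 9.5.2 falling short of 12/16 leads only to further studies. Fewer vaccines may themselves lower response, and no rewording changes that. The sample size, the 12/16 rule, its 61.5% limit and the DLT stopping boundary are unaffected. This is a minor correction, worth making because the samples at risk serve primary endpoints and the change costs almost nothing.

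**What to change.** In Section 5.4.2, replace *off the study* with *off protocol treatment*, the term already used in 5.5.4.

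In Section 5.5.2, add a sentence such as: *Participants who stop vaccines because of a DLT continue adverse-event follow-up and all remaining scheduled blood draws (through week 12, week 26, and weeks 52 and 104) unless they withdraw consent or start new therapy.* Biopsies stop as already written.

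The sentence should name weeks 52 and 104, since stopping at week 26 would invite sites to drop draws that nothing in 5.5.2 now removes. Limiting it to DLTs leaves the other discontinuation reasons, such as noncompliance, as they are.

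The cost is one phrase and one sentence in an amendment, with no new visits or assays. The downside is that about one participant who has stopped vaccines is asked to keep attending visits that are already planned.
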